## 3.4 Statistical Analyses

### 3.4.1 General Considerations

The statistical analyses will be performed under the responsibility of the Sponsor's Biostatistics platform using SAS® Version 9.4 or later.

The results of the statistical analysis will be available in the clinical study report (CSR).

For descriptive purposes, the following statistics will be presented:

**Table 3.1: Descriptive statistics produced**

Disposition and follow-up description	Categorical data	Number of participants. Percentage of participants.
	Continuous data	Mean, standard deviation, quartiles, minimum, and maximum.
Baseline characteristics	Categorical data	Number of participants. Percentage of participants.
	Continuous data	Mean, standard deviation, quartiles, minimum and maximum.
Clinical safety results	Categorical data	Solicited: Number and percentage (95% CIs) of participants. Unsolicited: Number and percentage (95% CIs) of participants and number of events.
Vaccine virus shedding results	Categorical data	Number and percentage (95% CIs) of participants.
	Continuous data	Mean and standard deviation, quartiles, minimum, and maximum.
Transmissibility results	Categorical data	Number and percentage (95% CIs) of participants.
Vaccine virus stability	Categorical data	Number and percentage (95% CIs) of participants.
Immunogenicity results	Categorical data (cutoff)	Number and percentage (95% CIs) of participants.
	Continuous data (titer / data)	Log10: Mean and standard deviation. Anti-Log10 (work on Log10 distribution, and anti-Log10 applied): Geometric mean, 95% CI of the geometric mean, quartiles, minimum, and maximum. Graphical representation by Reverse Cumulative Distribution Curve (RCDC)
Infectivity results	Categorical data	Number and percentage (95% CIs) of participants.
RSV WT infection	Categorical data	Number and percentage (95% CIs) of participants, number of events, and 95% CI.

The statistical methodology will be based on the use of two-sided 95% confidence intervals (CI).

All endpoints will be summarized by study intervention group. For the main parameters, 95% CI of point estimates will be calculated using the normal approximation for quantitative data and using the exact binomial distribution (Clopper-Pearson method) for proportions.

For immunogenicity data, assuming that Log10 transformation of the titers/titers ratio follows a normal distribution, at first, the mean and the 95% CI will be calculated on Log10 (titers/titers ratio) using the usual calculation for normal distribution (using Student's t distribution with n-1 degree of freedom), then antilog transformations will be applied to the results of calculations, in

order to provide geometric mean titers (GMTs) and geometric mean titers ratios (GMTRs) and their 95% CI.

$$GM \text{ is defined as follows: } GM = \left( \prod_{i=1}^n y_i \right)^{1/n} = 10^{\left( \frac{1}{n} \sum_{i=1}^n \log_{10}(y_i) \right)},$$

where  $(y_1, y_2, \dots, y_n)$  are the observed titers or individual ratios for each participant.

Viral shedding, vaccine virus stability (for pediatric participants receiving placebo and ad-hoc close contact participants), and safety analyses will be performed on the SafAS. Immunogenicity analyses and infectivity analyses will be presented on the FAS. Transmissibility analyses will be performed on the SafAS and PPAS as well as on other analysis set (ad-hoc close contact participants).

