Number of participants	100 pediatric participants 6 to < 24 months of age
Intervention groups	Eligible pediatric participants will be randomized in a 1:1 ratio to receive 2 intranasal administrations (56 days apart) of either the RSVt vaccine or placebo at D01 and D57
Total duration of study participation	Approximately 8 months for each pediatric participant. The duration of the ad-hoc close contacts will be limited to the Illness Visit.
Countries	United States and Puerto Rico
Use of an Independent Data Monitoring Committee, Dose Escalation Committee, or similar review group	NO

VAD00014 study is planned to enroll a convenience sample of 100 children aged 6 to < 24 months (hereafter referred as pediatric participants) at least by pairs or larger groups of children, living in a context in which the probability of transmission is maximized, ie, group of children attending daycare centers, twins, and children living with siblings of similar age. The pediatric participants will be randomized to receive either the RSVt vaccine or placebo (the placebo group will allow to assess the transmissibility and safety of the RSVt vaccine in a blinded way).

VAD00014 study will be randomized, observer-blind, placebo-controlled, and will include 2 administrations, 56 days apart (ie, at Day (D)01 and D57). Pediatric participants will be randomized in 1:1 ratio and are planned to be enrolled in pairs or in small groups (ie, siblings or attending the same daycare center) to ensure that transmissibility from pediatric participants receiving the RSVt vaccine to pediatric participants receiving the placebo can be evaluated. Shedding, transmissibility, and genetic stability of the vaccine virus will be assessed through the collection of nasal swabs at regular intervals after each study intervention administration. As RSVt vaccine will be administered by intranasal route, vaccine virus shedding is then expected in the nose. Therefore, nasal swabs are commonly used for shedding assessment, especially in the infant population in which nasal washes are more invasive.

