**Table 1.1: Design**

Type of design	Parallel, multi-center
Phase	II
Control method	Placebo-controlled
Study population	

Pediatric participants: Healthy infants / toddlers 6 to < 24 months of age in close contact with other infants / toddlers 6 to < 24 months of age who will participate in the study

Ad-hoc close contact participants: Ad-hoc close contact children and adults who experience acute respiratory illness (ARI) in the 28 days following the administration of the study intervention to the close contact pediatric participant

Level and method of blinding	Observer-blind: 

Blinding for study intervention group assignment: participants, parents or legally acceptable representative (LAR), outcome assessors, investigators, laboratory personnel, Sponsor study staff

No blinding for study staff who prepare and administer the study interventions

Study intervention assignment method	Pediatric participants will be screened for eligibility criteria at the time of inclusion and randomized to receive either RSVt vaccine or placebo in a 1:1 ratio. Randomization will be stratified by contact group (the household /group attended in daycare center) and by age group (< 12 months / ≥ 12 months)

Number of participants	100 pediatric participants 6 to < 24 months of age
Intervention groups	Eligible pediatric participants will be randomized in a 1:1 ratio to receive 2 intranasal administrations (56 days apart) of either the RSVt vaccine or placebo at D01 and D57
Total duration of study participation	Approximately 8 months for each pediatric participant. The duration of the ad-hoc close contacts will be limited to the Illness Visit.
Countries	United States and Puerto Rico
Use of an Independent Data Monitoring Committee, Dose Escalation Committee, or similar review group	NO

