### 3.2 Sample Size Determination

No sample size calculation was done as there are no statistical hypotheses in this study. A total of 100 pediatric participants (ie, 50 per study intervention group) are planned to be enrolled, based on clinical feasibility.

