### 3.4.2 Primary Endpoints

#### 3.4.2.1 Vaccine virus transmission

Presence of vaccine virus detected by RSVt qRT-PCR ( $\geq$ LOD) in nasal swabs after the first vaccination (D01, D04, D08, D11, D15, D18, and D22) will be summarized in pediatric participants receiving placebo with 95% CIs:

- Number and percentage of participants with vaccine virus detected at each timepoint
- Number and percentage of participants with vaccine virus detected in at least one nasal swab

Transmissibility analyses will be performed on the SafAS and PPAS. Vaccine virus transmission is defined in [Section 4.2.1](#).

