## 6.2 Appendix 2 Use the Reed-Frost models and Greenwood models to estimate the transmission probability.

The binomial model is often used to estimate the transmission probability based on the idea that exposure to infection occurs in discrete contacts. Generally,  $p$  is defined as the transmission probability during a contact between a susceptible person and an infectious person. The quantity  $q = 1 - p$  is the probability that the susceptible person will not be infected during the contact, called the escape probability. In this section, the susceptible person is considered the pediatric participant who received placebo, and an infectious person is considered the pediatric participant who received RSVt vaccine.

Chain binomial models are dynamic models developed from the simple binomial model by assuming that infection spreads from individual to individual in populations in discrete units of time, producing chains of infection governed by the binomial probability distribution. The Reed-Frost and Greenwood models are examples of chain binomial models. To use these models, the number of susceptible persons and the number of infectious persons involved in each transmission generation should be known. However, in this study, the actual transmission chains is not observed, thus a single transmission generation is considered.

A contact group is defined as a group of pediatric participants who live in the same household or who attend in the same daycare center. A contact group is considered as a transmission unit and different contact groups are assumed to be separate and independent of one another. A total of  $J$  contact groups is assumed.  $S_j$  and  $I_j$  are the number of pediatric participants who received placebo and the number of pediatric participants who received RSVt vaccine in the  $j$ th contact group, respectively.  $X_j$  is the total number of pediatric participants who received placebo and have detective vaccine virus in the  $j$ th contact group.

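### The planned interval for the transmission proportion treats placebo children in the same contact group as independent and can cover less than 95% when groups hold several placebo children

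*SAP*

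**What the plan says.** SAP 3.4.1 (Table 3.1 and the text below it) and Protocol 9.3.1 set two-sided 95% intervals throughout, calculated "using the exact binomial distribution (Clopper-Pearson method) for proportions". SAP 3.4.2.1 applies this to the primary transmission endpoint in placebo recipients, at each timepoint and as "Number and percentage of participants with vaccine virus detected in at least one nasal swab". SAP 3.4.3.3 does the same after the second administration. The unit is the participant in every case. No section adjusts for contact group or plans a group-level proportion.

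The design is grouped. Protocol 4.1 enrols children "at least by pairs or larger groups of children, living in a context in which the probability of transmission is maximized". SAP Table 1.1 adds: "Randomization will be stratified by contact group (the household /group attended in daycare center) and by age group". SAP Appendix 2 states: "A contact group is considered as a transmission unit and different contact groups are assumed to be separate and independent of one another". Its worked Reed-Frost example has two placebo and three vaccinated children in one group. SAP 3.2 gives the size: "A total of 100 pediatric participants (ie, 50 per study intervention group) are planned to be enrolled, based on clinical feasibility".

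**The concern.** Clopper-Pearson limits are exact for independent outcomes with a common probability. Placebo children in one playroom or household are exposed to the same vaccinees and the same amount of shedding, and one placebo child could infect another. Their outcomes are therefore likely to be positively correlated. Appendix 2 recognises this structure, but the primary interval does not use it.

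The study tests no hypothesis and its size rests on feasibility, so readers will judge the transmission result largely by its interval. SAP 3.5 sends the interim transmission results to Health Authorities before Phase III. If few or no positives are seen, the upper limit will be read as the transmission rate that has been ruled out.

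**Working it through.** **Inputs from the documents.** Two-sided 95% Clopper-Pearson (SAP 3.4.1); 50 placebo children planned (SAP 3.2); allocation 1:1 (SAP Table 1.1). The plan states no precision, so there is no figure of its own to reproduce.

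**Assumptions.** Placebo children per group (m) and the ICC are not in the documents. Both are varied. Outcomes within a group follow a beta-binomial distribution.

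**Step 1: the planned interval if children are independent.** With x = 0 the upper limit is 1 − 0.025^(1/n).
- 0/50: 1 − 0.025^(1/50) = 7.1%
- 2/50: 0.5% to 13.7%
- 5/50: 3.3% to 21.8%

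**Step 2: coverage of that interval under clustering.** The distribution of the total number of positives is the convolution of the group distributions. Coverage is the probability of those totals whose Clopper-Pearson interval contains the true rate. At a true rate of 10%:

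| Placebo children per group | ICC 0 | 0.1 | 0.2 | 0.4 |
|---|---|---|---|---|
| 25 groups of 2 | 97.0% | 96.2% | 95.4% | 93.6% |
| 25 groups of 1 plus 5 groups of 5 | 97.0% | 95.4% | 93.8% | 90.9% |
| 10 groups of 5 | 97.0% | 93.8% | 90.4% | 82.8% |

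For the middle layout, coverage at ICC 0.1, 0.2 and 0.4 is 97.9%, 96.9% and 95.0% at a 5% rate, and 94.8%, 92.9% and 88.7% at a 20% rate. With one placebo child in every group, nothing changes.

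**Step 3: which limit misses.** For ten groups of 5 at ICC 0.2 and a 10% rate, 9.6% of intervals miss. In 2.5% the upper limit lies below the truth, which is the nominal tail. In 7.1% the lower limit lies above it. The upper-limit error exceeds 2.5% at ICC 0.4 (6.5%), and at a 20% rate already at ICC 0.1 (3.8%).

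**Step 4: no positives.** Design effect DE = 1 + (m − 1) × ICC; effective n = 50/DE. For unequal groups m is replaced by Σm²/Σm, which for the middle layout is (25 × 1 + 5 × 25)/50 = 3. At ICC 0.2:
- two per group: DE 1.2, effective n 41.7, limit 8.5%
- mixed layout: DE 1.4, effective n 35.7, limit 9.8%
- five per group: DE 1.8, effective n 27.8, limit 1 − 0.025^(1/27.8) = 12.4%

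Direct check for five per group at ICC 0.2. The beta parameters sum to (1 − 0.2)/0.2 = 4. At a true rate of 7.11%, one group has no positives with probability (3.716/4)(4.716/5)(5.716/6)(6.716/7)(7.716/8) = 0.772. All ten groups have none with probability 0.772^10 = 7.5%, where the interval assumes 2.5%. That probability falls to 2.5% at a rate of about 10.0%: (0.90 × 0.92 × 0.933 × 0.943 × 0.95)^10 = 0.692^10 ≈ 0.025. The planned limit is therefore too low in this scenario. The design-effect limit of 12.4% errs on the cautious side.

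**Step 5: group-level limits.** 0/25 groups gives an upper limit of 13.7%, and 0/10 groups gives 30.8%. These bound the chance of any transmission in a group, not the per-child rate.

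**The case against.** The strongest reply is that Clopper-Pearson is conservative and that groups may be small. Protocol 4.1 also speaks of pairs and small groups, and Protocol 4.2 and 10.1.3 favour twins. Ten groups of 5 placebo children would imply about ten participating children per group at 1:1 allocation. With 30 single-placebo groups and ten groups of two, coverage at a 10% rate stays at 95.8% or above up to ICC 0.4. This stands, and it limits the size of the problem. It does not remove the problem, because the plan sets no maximum group size. Nor do the documents guarantee one placebo child per pair: strata combine contact group and age group, so a pair on either side of 12 months falls into two strata.

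A second reply is that Appendix 2 already supplies a group-based analysis. It does plan a 95% interval for the transmission probability. But it is exploratory, and both likelihoods treat placebo children within a group as independent given p. The Greenwood likelihood reduces to p^ΣX × q^Σ(S−X), the same pooled binomial, so it does not repair the primary interval.

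A third reply is that a descriptive study has no error rate to protect. That is correct for testing. An interval labelled 95% should still be close to 95%.

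**Conclusion.** The concern holds as a conditional one. The per-child interval ignores contact groups, and it can under-cover if groups hold several placebo children with positively correlated outcomes. At a 10% rate the scenarios run from no material loss (two per group, ICC up to 0.2) to 82.8% coverage (ten groups of 5, ICC 0.4). All of this rests on assumed group sizes and ICCs.

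A reader might infer more than the documents support:
- **That the interval is too narrow wherever a group has several placebo children.** With two per group and ICC 0.1, coverage is still 96.2%.
- **That every loss of coverage means transmission is understated.** Many misses at a 10% rate are at the lower limit. The low upper limit is clearest with zero or few positives.
- **That this interval is the trial's only measure of uncertainty.** Appendix 2 plans another.
- **That 30.8% for 0/10 groups is the corrected form of 7.1%.** It answers a different question.

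With no decision threshold in the plan and an unknown size of effect, this should be fixed, but it is not a fatal flaw.

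**What to change.** Keep the point estimates, and amend SAP 3.4.2.1 and 3.4.3.3 as follows.

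1. Tabulate the number of placebo children and vaccinees per contact group.
2. Add the proportion of contact groups with any positive placebo child, among groups with at least one vaccinee and one placebo child. Give it an exact group-level interval and label it as a separate estimand.
3. When positives occur, give a contact-group-adjusted interval for the per-child proportion: Clopper-Pearson with n and x both divided by the design effect. Name the ICC estimator in advance and say how a negative estimate is handled, because the estimate will be unstable with few positives.
4. With no positives the ICC cannot be estimated. Show the group-level limit beside 0/n, and the per-child limit over a stated range of ICCs.

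The contact-group number is already part of the participant identifier (Protocol 6.3.1), so the grouping needs no new data. The identifier is not shown to record household or daycare, so a split by setting would need that recorded separately. The cost is SAP wording, one more table and wider intervals.

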### 3.4.2 Primary Endpoints

#### 3.4.2.1 Vaccine virus transmission

Presence of vaccine virus detected by RSVt qRT-PCR ( $\geq$ LOD) in nasal swabs after the first vaccination (D01, D04, D08, D11, D15, D18, and D22) will be summarized in pediatric participants receiving placebo with 95% CIs:

- Number and percentage of participants with vaccine virus detected at each timepoint
- Number and percentage of participants with vaccine virus detected in at least one nasal swab

Transmissibility analyses will be performed on the SafAS and PPAS. Vaccine virus transmission is defined in [Section 4.2.1](#).

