**Table 1.2: Schedule of activities for pediatric participants**

Phase II Study, 11 Planned Visits, 2 Vaccinations, 3 Blood Samples, 9 Planned Nasal Swabs, One 6-Month Safety Follow-up Phone Call, approximately 8 Months' Duration Per Pediatric Participant

Visit/Contact*	Collection of information in the CRF	V01	V02	V03	V04	V05	V06	V07	V08	V09	V10	V11	Safety followup phone call	Illness Visit‡‡
Study timelines days (D)		D01	D04	D08	D11	D15	D18	D22	D57	D64	D71	D85	D237	
Visit Interval			V01 + 3d	V01 + 7d	V01 + 10d	V01 + 14d	V01 + 17d	V01 + 21d	V01 + 56d	V08 + 7d	V08 + 14d	V08 + 28d	V08 + 6 months	
Time windows (days)		NA	[+1]	[+1]	[+1]	[+1]	[+1]	[+1]	[+7]	[+1]	[+1]	[+7]	[+14]	
Visit procedures:														
Informed consent	X	X												
Inclusion/exclusion criteria	X	X												
Collection of demographic data	X													
Collection of medical history	X Significant Medical History	X												
Physical examination	X	X							X					
Vital signs†	X	X							X					
Rapid COVID-19 test	X	X							X					

Visit/Contact*	Collection of information in the CRF	V01	V02	V03	V04	V05	V06	V07	V08	V09	V10	V11	Safety followup phone call	Illness Visit‡‡
Study timelines days (D)		D01	D04	D08	D11	D15	D18	D22	D57	D64	D71	D85	D237	
Visit Interval			V01 + 3d	V01 + 7d	V01 + 10d	V01 + 14d	V01 + 17d	V01 + 21d	V01 + 56d	V08 + 7d	V08 + 14d	V08 + 28d	V08 + 6 months	
Time windows (days)		NA	[+1]	[+1]	[+1]	[+1]	[+1]	[+1]	[+7]	[+1]	[+1]	[+7]	[+14]	
Collection of reportable concomitant medications/vaccinations	X								X					X
Randomization/allocation of participant number	X	X												
Dose number	X	X							X					
Blood sampling (BL) [5 mL]	X	BL0001 Pre-vac1							BL0002 Pre-vac2			BL0003		
Nasal swab (NS)‡	X	NS0001 Pre-vac1	NS0002	NS0003	NS0004	NS0005	NS0006	NS0007		NS0008	NS0009			UN0001 to UN000X
Vaccination (vac)	X	VAC1							VAC2					
Immediate surveillance (30 min)§	X	X							X					
DC provided**		DC1							DC2					
DC reviewed††			DC1	DC1	DC1	DC1	DC1	DC1	DC1	DC2	DC2	DC2		
DC collected									DC1			DC2		
MA provided												MA		
MA reviewed												MA		
Collection of solicited administration site and systemic reactions	X	From D01 to D22							From D57 to D78					

Visit/Contact*	Collection of information in the CRF	V01	V02	V03	V04	V05	V06	V07	V08	V09	V10	V11	Safety followup phone call	Illness Visit†‡
Study timelines days (D)		D01	D04	D08	D11	D15	D18	D22	D57	D64	D71	D85	D237	

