## 3 Statistical Considerations

### 3.1 Statistical Hypotheses

All analyses will be descriptive, no hypothesis will be tested.

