#### 3.4.2.3 Vaccine virus stability

Presence of any vaccine virus variation will be described in pediatric participants receiving placebo and ad-hoc close contact participants:

- Number and percentage of participants with any variation in genetic sequence of ΔNS2, Δ1313, and I1314L segment of the vaccine virus compared to the reference strain vaccine virus isolates in the nasal swabs with detected vaccine virus (vaccine virus shedding by qRT-PCR  $\geq$  LOD).

Vaccine virus stability analysis will be performed on the SafAS .

The vaccine virus stability will be described as well in a random subset of pediatric participants receiving RSVt vaccine based on SafAS.

In order to organize the segment sequencing, a listing of samples to be sequenced is to be provided to the laboratory. The laboratory personnel must remain blinded therefore there should be no mention of the vaccine group in this listing. The nasal swab samples to be tested will be selected as follows:

- Any nasal swab with detected vaccine virus from a participant who received placebo at the previous vaccination and from ad-hoc close contact participants.
- The latest post-vaccination 1 nasal swab with detected vaccine virus among a subset (selected randomly) of 20 participants who received RSVt vaccine at the 1st vaccination and with detected vaccine virus in at least 1 nasal swab.  
Note: a subset of 10 participants randomly selected as defined above among the participants involved in the first interim analysis will be part of the first interim analysis
- The latest post-vaccination 2 nasal swab with detected vaccine virus in any participants who received RSVt vaccine at the 2nd vaccination and with detected vaccine virus in at least 1 nasal swab.

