### 3.5 Interim Analyses

- An unblinded interim analysis will be performed on available data collected from D01 (V01) to D22 (V07) for participants randomized on or before 21July2023, in two steps:
  - The first step will be performed on available shedding / transmission data by RSVt qRT-PCR assay up to 21 days after the first study intervention administration, that will also include baseline immunogenicity data, safety data up to 21 days after the first study intervention administration, in order to share preliminary data to Health Authorities before moving to phase III clinical development. Randomization code will be broken for the Sponsor but blinding will be maintained at sites and participants/parents levels. Some listings will be generated to define the next steps for nasal swab testing (sequencing, plaque assay and WT RT-PCR).
  - The second step will be performed when subsequent data up to 21 days after the first study intervention administration will be available (e.g. segment sequencing, plaque assay and WT RT-PCR data).
- An additional unblinded interim analysis will be performed once all data collected from D01 (V01) to D22 (V07) from all participants is available. A two-step process of analysis will also be applied.
- The final unblinded statistical analysis will address the objectives on all participants  
No statistical adjustment is necessary because no hypotheses will be tested.  
This study will not include an early safety data review.

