### 4.2 Complementary Information on Derived Endpoints: Calculation Methods

#### 4.2.1 Vaccine Virus Transmission

Vaccine virus transmission is defined as presence of detected vaccine virus confirmed by RSVt qRT-PCR assay (vaccine virus shedding  $\geq$  LOD) in pediatric participants receiving placebo and ad-hoc close contact participants.

Detected viable RSV virus is defined as values from the plaque assay  $\geq$  LOD.

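### The primary transmission count accepts one PCR detection in any listed swab, including the pre-dose D01 swab, and no readable rule separates corroborated from single-signal cases

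*SAP*

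**What the plan says.** **Case rule.** SAP 3.4.2.1 summarises, in placebo recipients, the "Number and percentage of participants with vaccine virus detected in at least one nasal swab", with detection meaning a result at or above the LOD. SAP 4.2.1 reads "Vaccine virus transmission is defined as presence of detected vaccine virus confirmed by RSVt qRT-PCR assay". The confirmation named there is the same PCR, not a second test. Protocol 4.2 defines transmission by that assay alone.

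**Swabs covered.** The endpoint uses detections "in nasal swabs after the first vaccination (D01, D04, D08, D11, D15, D18, and D22", seven swabs in all. The schedule in SAP Table 1.2 labels the D01 swab "NS0001 Pre-vac1", so it precedes dosing. SAP 4.2.3 (infectivity) lists only D04 to D22 as post-vaccination 1 samples.

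**Other laboratory data.** SAP 3.4.2.3 selects for sequencing "Any nasal swab with detected vaccine virus from a participant who received placebo at the previous vaccination and from ad-hoc close contact participants", for the stability endpoint. SAP 4.2.1 also defines viable virus by plaque assay, but does not make it part of the transmission definition.

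**Interim timing.** Under SAP 3.5, step 1 reports PCR shedding and transmission so that preliminary data can go to Health Authorities before Phase III. Sequencing, plaque assay and wild-type RT-PCR follow: "The second step will be performed when subsequent data up to 21 days after the first study intervention administration will be available". The later interim analysis of all participants uses the same two steps.

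**The concern.** With 50 placebo children, the transmission result may rest on one or two PCR signals. An any-swab rule gives each child several chances of a false detection, so the child-level error is close to the per-swab error times the number of swabs. Nothing readable tells the analyst how to present a child with one isolated detection near the LOD differently from a child with repeated detections or vaccine-virus sequence. Both count as one case.

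A single false case changes the reported result from no transmission seen to transmission occurred, and step 1 would report it before the follow-up testing is available. The same detections supply the count X_j in the Reed-Frost and Greenwood likelihoods (SAP Appendix 2) and the age-group transmission analyses (SAP 3.4.5).

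Read literally, the swab list also lets a pre-dose D01 signal count as transmission from study vaccination, which is impossible.

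**Working it through.** The plan has no calculated figure to reproduce. SAP 3.2 states: "A total of 100 pediatric participants (ie, 50 per study intervention group) are planned to be enrolled, based on clinical feasibility". No expected transmission rate, assay specificity or precision target is given.

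**Inputs**
- n = 50 placebo children (SAP 3.2).
- k = 6 post-dose swabs, D04 to D22, or k = 7 as listed (SAP 3.4.2.1).
- f = per-swab false-positive rate: not in the documents. Assumed range 0.05% to 1%.
- t = true transmission rate: not in the documents. Assumed range 1% to 10%.
- Errors independent between swabs, and sensitivity 1: assumptions.
- 95% CIs by Clopper-Pearson (SAP 3.4.1).

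**Step 1: false cases with six post-dose swabs.** Child-level risk = 1 − (1 − f)^6. Expected false cases = 50 × that risk. Chance of at least one = 1 − (1 − f)^300, since 6 × 50 = 300 (this takes none of the 50 as truly infected).

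| Per-swab specificity | Child-level risk | Expected false cases | Chance of at least one |
|---|---|---|---|
| 99.0% | 5.85% | 2.93 | 95% |
| 99.5% | 2.96% | 1.48 | 78% |
| 99.9% | 0.60% | 0.30 | 26% |
| 99.95% | 0.30% | 0.15 | 14% |

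**Step 2: counting D01 as well (k = 7).** The chance of at least one false case becomes 83% at 99.5%, 30% at 99.9% and 16% at 99.95%.

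**Step 3: effect on the reported result.** 0/50 has a 95% CI of 0 to 7.11%; 1/50 has 0.05% to 10.65%.

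**Step 4: share of positive children who are false (k = 6).** With FP the child-level risk from step 1, share = (1 − t)FP / [t + (1 − t)FP].

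| True rate | f = 0.1% | f = 0.5% |
|---|---|---|
| 1% | 37% | 75% |
| 2% | 23% | 59% |
| 5% | 10% | 36% |
| 10% | 5% | 21% |

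False cases exceed half when FP > t/(1 − t). At t = 2%, FP must exceed 0.02/0.98 = 2.04%, so f must exceed 1 − (1 − 0.0204)^(1/6), about 0.34%.

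**Step 5: what a second positive swab adds.** The chance of two or more false swabs in one child is 1 − (1 − f)^6 − 6f(1 − f)^5. At f = 0.5% this is 0.037%, or 0.0185 expected cases in 50. At f = 0.1% it is 0.0015%, or 0.0007 cases.

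**Step 6: D01 as a background check.** If none of 100 pre-dose swabs is positive, the upper 95% limit is 3.62% per swab. Over six swabs that allows 1 − (1 − 0.0362)^6 = 19.9% per child. The check is therefore weak.

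**The case against.** **Withheld text.** The assay description under Protocol 8.1.2 and the exploratory sections (Protocol 9.3.4, SAP 3.4.4) are largely unreadable in the public version. Retest rules, controls or a viable-virus output may sit there. A reader might infer that the corroborating data are never used. The documents support only that the readable primary definition does not use them.

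**Expected rate.** A reader might infer that transmission was expected to be near zero. Neither document says so, and Protocol 4.1 describes a setting chosen to maximise transmission.

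**Dominance.** A reader might infer that false positives would make up most cases. That depends on two unknown inputs: at 99.9% specificity and a true rate of 2%, 77% of positive children are real. Clustered contamination, for example by laboratory batch or household, would also lower the chance of at least one false case for the same per-swab error, while making the count more variable.

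**Carry-over.** Sequencing or plaque assay of a specimen contaminated at collection by a vaccinated contact would still show vaccine virus. Only a second positive swab speaks to this. The schedule allows home visits by a site nurse but does not say that one nurse swabs both children.

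**Already planned.** SAP 3.4.2.2 tabulates detection and quantified shedding by group at each timepoint, D01 included.

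**Purpose.** SAP 3.1 says "All analyses will be descriptive, no hypothesis will be tested". For unintended spread, a sensitive any-positive rule is the cautious choice.

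All of this stands and limits the claim. It does not supply a child-level rule for corroboration, or remove D01 from the primary list.

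**Conclusion.** The point holds in limited form. The any-swab rule is defensible as the cautious primary estimate, but it literally includes a pre-dose swab, and the readable plan has no prespecified way to show how many cases are supported by more than one signal. Interim step 1 reports PCR transmission before sequencing and plaque data exist.

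The size is conditional. It rests on assumed specificity, independent errors, six swabs and 50 children. Within 99.5% to 99.95% specificity, the expected number of false cases runs from 1.5 down to 0.15. Even at 99.9% there is roughly a one-in-four chance of at least one. Whether false cases would outnumber true ones cannot be determined from the documents. The estimate should be revisited if the withheld assay text gives specificity or retest rules.

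**What to change.** 1. In SAP 3.4.2.1, limit the any-swab count to D04–D22 and keep it as the primary estimate. Cite D01 positivity, already tabulated under SAP 3.4.2.2, as a weak background check. Protocol sections 3 and 9.3.2 carry the same swab list, so record the clarification in SAP section 5.
2. In SAP 4.2.1, prespecify a supportive count of *corroborated transmission*: qRT-PCR at or above the LOD plus at least one of (a) a second positive swab from the same child, (b) vaccine-virus sequence in the planned sequencing, or (c) plaque assay at or above its LOD, where performed.
3. State which criterion each case met, because only (a) speaks to carry-over at collection. Add a *not confirmable* category for low-titer samples that cannot be sequenced.
4. Report both counts with 95% CIs for dose 1, dose 2 and ad-hoc contacts.
5. Label interim step-1 positives *pending corroboration* and update them at step 2.

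The cost is SAP wording and a few table rows. The criteria use swabs and assays already planned. The drawback is that a true but brief or low-titer transmission may go uncorroborated, which is why both rows are kept. The rule should be written before further unblinded results are seen, or it will look data-driven.
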